8.1 Statistical Analysis

Statistical analysis will be performed by a consulting statistician contracted with EvergreenHealth and whose services we have used on recent studies in PD. All data will remain blinded throughout the data analysis and will be unblinded only in the event of a medical emergency.

8.2 Sample Size Considerations

This is a prospective, double-blinded, randomized controlled pilot study. The purpose is to test a hypothesis in a preliminary fashion and to assess for safety in this population with a specific neurological disease. As such, a power calculation may be irrelevant. However, a small number of subjects (e.g. less than 10) may cause significant sampling error to miss a treatment effect or common safety issue. Some entities that establish criteria for level of evidence consider a sample size of 20 subjects in each arm to be a minimum representative population to be considered for Class III or better classification of Level of Evidence. This will be achieved by having 20 subjects complete both treatment and placebo arms using a crossover study design. Therefore, a sample size of 20 subjects is a reasonable number for a pilot study of this nature.

8.3 Study Population

The study population will include all patients who pass screening and undergo randomization. Data will be analyzed in an intent-to-treat fashion.

8.4 Baseline and Demographic Characteristics

The following characteristics will be summarized descriptively for placebo and drug groups:

- Demographics (age, gender, race)
- Parkinson disease characteristics at baseline (disease duration, date of onset, initial symptom, modified Hoehn and Yahr stage in the ON state, and MDS-UPDRS part 3 score in the ON state)
- Levodopa-equivalent daily dose (LEDD), calculated according to published formulae (Tomlinson 2010, Rytary Prescribing Information, Duopa Prescribing Information).

8.5 Efficacy Analysis

Analysis of primary and secondary outcome measures will include:

- Summary statistics (n, mean, standard deviation, median, minimum and maximum) at baseline, Office Visit 3 and Office Visit 5 by treatment.
- For clinical rating scales, summary of % change from baseline to Office Visit 3, from baseline to Office Visit 5, and from Office Visit 4 to Office Visit 5, by treatment
- For PSG variables, summary of % change from PSG 1 to PSG 2 and from PSG 1 to PSG 3, by treatment

- For wearable sleep monitor, summary of % change in total hours of sleep and WASO. Mean over the week prior to Office Visit 2 (baseline) will be compared to the mean over the final week of Treatment Period 1 and to the mean over the final week of Treatment Period 2. Mean over the week prior to Office Visit 4 (during washout) will be compared to the mean over the final week of Treatment Period 2. This will be done by treatment arm.
- Significance testing

Outcome measures will be compared between groups using analysis of covariance (ANCOVA) or other method as deemed appropriate by the consulting statistician. Demonstration of superiority will depend on achieving statistical significance for the primary endpoint. Level of significance will be defined as $p = 0.05$. All statistical tests will be two-sided.

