1.5 Study Overview

The proposed study is a randomized, double-blind, placebo-controlled, cross-over trial to assess the safety, tolerability, and efficacy of suvorexant specifically in a cohort of 20 PD patients between the ages of 30 and 80 (inclusive) who have a complaint of insomnia. After informed consent is given, potential subjects will be screened to ensure they meet eligibility criteria. This will include an overnight polysomnogram (PSG), which will serve both as a baseline and a screening PSG. Active drug will be suvorexant 10 mg po QHS with an optional up-titration to 15 mg po QHS after 2 weeks. The first treatment period will be 4 weeks long, in which subjects will be randomized 1:1 to receive active drug or matching placebo. At the end of treatment period 1, subjects will undergo efficacy assessment with repeat PSG and clinical scales. This will be followed by a 2-week washout period with placebo; this period only will be single-blinded, as subjects only will be blinded to treatment. Subjects will then be crossed over into the alternate treatment group, which will once again be double-blinded; those on active treatment for period 1 will be switched to placebo, and those on placebo in period 1 will be switched to active treatment. Treatment period 2 will also be 4 weeks long, and at the end of this, subjects will undergo final assessment with PSG and clinical scales.

All subjects, whether in placebo or active arm, will receive a wearable sleep monitor to be worn continuously throughout the study. The subjects will be allowed to keep the wearable sleep monitor in lieu of a monetary reimbursement for Office Visit 1; subjects will receive a small monetary reimbursement per visit for each office visit after Office Visit 1.

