4.5 Washout Period (Office Visit 3)

Office Visit 3 will occur within 7 days after PSG 2. In addition to PSG review, medications will be reviewed again to ensure stability of the PD medication regimen and absence of any prohibited medications. Any possible adverse events (AEs) will be assessed. General physical exam will be performed, including vital signs (blood pressure, heart rate, and respiratory rate).

PD symptoms and signs will be assessed with the complete MDS-UPDRS. Study scales (MoCA, ISI, ESS, BDI, BAI, CGI-C, SGI-C, C-SSRS) will be administered. Data from the wearable

sleep monitor will be collected. Laboratory testing will be performed as deemed appropriate by the investigator.

A new supply of study pills will be dispensed. For the washout period, all subjects will be given the placebo matching the dose being administered most recently (i.e. in the second half of treatment period 1).

4.6 Treatment Period 2

4.6.1 Office Visit 4

Office Visit 4 will occur 2 weeks (11-18 days) after Office Visit 3 and will mark the beginning of treatment period 2. Medications will be reviewed again to ensure stability of the PD medication regimen and absence of any prohibited medications. Any possible adverse events (AEs) will be assessed.

To serve as baseline scores for treatment period 2, PD symptoms and signs will be assessed with the complete MDS-UPDRS and study scales (MoCA, ISI, ESS, BDI, BAI, CGI-C, SGI-C) will be administered. Data from the wearable sleep monitor will be collected. Laboratory testing, including urine hCG, will be performed as deemed appropriate by the investigator.

A new supply of study pills will be dispensed in a crossover fashion. All subjects who received study drug in treatment period 1 will be given placebo in treatment period 2, and all subjects who received placebo in treatment period 1 will be given study drug in treatment period 2. For treatment period 2, double-blinding will be resumed. Initial dose for all subjects will be 10 mg qhs.

4.6.2 Phone Visit 4

Phone Visit 4 will occur 3-4 days after Office Visit 4 to review safety and tolerability through questioning about adverse events.

4.6.3 Phone Visit 5: Titration in Treatment Period 2

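### For the rating scales and wearable outcomes, period-2 change from Office Visit 4 or the washout week uses a post-randomisation baseline confounded with prior treatment; it should not carry the treatment comparison

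*Combined protocol and SAP*

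**What the plan says.** Section 8.5, repeated in 1.11, plans three percentage-change summaries for the rating scales: baseline to Office Visit 3, baseline to Office Visit 5, "and from Office Visit 4 to Office Visit 5, by treatment". For the wearable monitor it adds, by treatment arm: "Mean over the week prior to Office Visit 4 (during washout) will be compared to the mean over the final week" of period 2. The polysomnographic variables use PSG 1 as the only baseline.

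Section 4.6.1 gives Office Visit 4 its role: "To serve as baseline scores for treatment period 2, PD symptoms and signs will be assessed with the complete MDS-UPDRS and study scales". The same section fixes who is in each period-2 arm: "All subjects who received study drug in treatment period 1 will be given placebo in treatment period 2". The other sequence is the mirror image, moving from placebo to suvorexant.

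On the washout, section 1.5 states: "This will be followed by a 2-week washout period with placebo". Section 4.6.1 sets the timing: "Office Visit 4 will occur 2 weeks (11-18 days) after Office Visit 3".

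For inference, the same list in 8.5 includes significance testing. Between-group comparison is by ANCOVA or another method that the statistician thinks suitable. No covariate is named, and no period, sequence or carry-over term is given. Summary statistics are listed for baseline, Office Visit 3 and Office Visit 5. No summary of change from baseline to Office Visit 4, or to the washout week, is listed.

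**The concern.** A change score compares treatments fairly only if its starting value is unaffected by treatment. In this contrast it need not be. The period-2 placebo arm consists of the subjects who have just come off suvorexant, and the period-2 suvorexant arm of those who have had only placebo. If anything of period 1 is left at Office Visit 4, it moves the starting value in one arm only. A residual benefit makes placebo subjects appear to deteriorate and exaggerates the drug effect; a rebound makes them appear to improve and shrinks it.

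At stake is a second period-2 result for each scale and wearable outcome, in which drug effect, residual effect and rebound cannot be separated. Because 4.6.1 calls Office Visit 4 the period-2 baseline and 8.5 names no covariate, the same value is also an obvious candidate covariate for the ANCOVA. A between-group comparison within period 2 also gives up the within-subject precision of the crossover on which section 8.2 rests its 20 subjects.

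**Working it through.** The plan gives no figure for this contrast: no effect size, SD, correlation or carry-over value. There is nothing to reproduce, so the check is algebra plus an illustration.

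**Model.** Let τ be the true effect (suvorexant minus placebo), and let c4 and c5 be what remains of period-1 suvorexant at Office Visits 4 and 5. Period effects common to both sequences cancel. Expected scores around a common mean μ:

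| Sequence | Baseline | Visit 3 | Visit 4 | Visit 5 |
|---|---|---|---|---|
| Suvorexant then placebo | μ | μ+τ | μ+c4 | μ+c5 |
| Placebo then suvorexant | μ | μ | μ | μ+τ |

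**What each analysis estimates.**
- Raw change, Visit 4 to 5: τ - (c5 - c4) = τ + c4 - c5.
- ANCOVA of Visit 5 on Visit 4 with slope b: τ + b·c4 - c5.
- Period-specific changes pooled over both periods: ½(τ + c4 - c5) + ½τ = τ + ½(c4 - c5).
- Change from pre-randomisation baseline to Visit 5: τ - c5.
- Within-subject Visit 3 against Visit 5: ½(τ - c5) + ½τ = τ - ½c5.

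**Illustration** (all values assumed): ISI mean 18, τ = -3, b = 0.6.

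| c4, c5 | Raw 4-5 | ANCOVA on Visit 4 | Pooled changes | Baseline-5 | Within-subject |
|---|---|---|---|---|---|
| -2, 0 | -5.0 | -4.2 | -4.0 | -3.0 | -3.0 |
| +2, 0 | -1.0 | -1.8 | -2.0 | -3.0 | -3.0 |
| -2, -1 | -4.0 | -3.2 | -3.5 | -2.0 | -2.5 |
| -2, -2 | -3.0 | -2.2 | -3.0 | -1.0 | -2.0 |

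With c4 = -2 and c5 = 0, slopes of 0.3 and 0.8 give ANCOVA estimates of -3.6 and -4.6, so 30% to 80% of the shift enters. Simulation (20,000 runs, 10 subjects per sequence, SD 4, correlations 0.3 to 0.8) agreed with these formulas to within 0.03 points.

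**Percentage change, as planned** (on the means, c5 = 0). Suvorexant: (15 - 18)/18 = -16.7%. With c4 = 0, placebo is 0% and the true difference is -16.7 points.
- c4 = -2: placebo (18 - 16)/16 = +12.5%; difference -29.2; bias -12.5.
- c4 = +2: placebo (18 - 20)/20 = -10.0%; difference -6.7; bias +10.0.

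A 2-point shift is 2/18 = 11.1% of baseline, so the bias is 10.0/11.1 = 0.9 to 12.5/11.1 = 1.1 times the shift.

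**Timing.** Appendix 11.1 puts Office Visit 3 at 0-7 days after PSG 2, and Office Visit 4 follows 11-18 days later. PSG 2 to Office Visit 4 is therefore 11 to 25 days. At the short end, the wearable's washout week starts about 11 - 7 = 4 days after PSG 2, the last night of period 1.

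**Precision.** At an assumed within-subject correlation of 0.5, the SD of a change equals the SD of a single score.
- Period-2 contrast, 10 v 10: half-width = t(0.975, 18) × √(2/10) = 2.101 × 0.447 = 0.94 SD.
- Within-subject contrast, 20 subjects: 2.101/√20 = 0.47 SD.

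The variance ratio is (0.94/0.47)² = 4. It applies equally to baseline-to-Visit 5 by treatment, so it is the cost of a parallel comparison and not of the Office Visit 4 baseline.

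**The case against.** The strongest reply is that the reach is small and that no contrast is immune. The affected items are one of three scale summaries and one wearable comparison, all secondary, in a declared exploratory study. Superiority rests on the primary endpoint alone. Every subject has a placebo washout, and section 2.2 reports a belief that rebound is not a risk. All of this limits the consequence. It does not show that the shift is zero, and no listed summary of the repeated scales or the wearable would check it.

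A reader might infer several stronger things that the documents do not support:
- **That the shift enters one for one.** This is exact only for raw change with nothing left at Office Visit 5. The plan specifies percentage change and names ANCOVA. The listed changes can also be read as period-specific changes pooled over all 20 subjects, which carry half.
- **That the pre-randomisation baseline gives a clean period-2 result.** It does so only if carry-over has gone by Office Visit 5. With c4 = c5 = -2, the Visit 4-5 raw change is the unbiased one (-3.0), against -1.0 from baseline and -2.0 within subject. Deleting the Visit 4-5 contrast outright is therefore a trade-off.
- **That the Office Visit 4 baseline itself costs fourfold variance.** The parallel comparison does, from either baseline.
- **That return to baseline is never looked at.** SGI-C and CGI-C are rated at Office Visit 4 against the start of the study (7.3.3, 7.3.4). What is missing is a listed baseline-to-Visit 4 summary for the other scales and the wearable.

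**Conclusion.** The point holds for the secondary rating scales and wearable outcomes. The Office Visit 4 to 5 and washout-week to period-2 changes by treatment use a post-randomisation baseline that is confounded with prior treatment. On raw change the bias is c4 - c5. If the effect has gone by Office Visit 5, that is the full shift for raw change, about 0.9 to 1.1 times it for percentage change in the example, 30% to 80% of it under ANCOVA on Office Visit 4 with slopes of 0.3 to 0.8, and half of it if changes are pooled over both periods.

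The documents give no value for the shift, SD, slope or correlation, so these sizes are illustrations and not predictions. The primary endpoint has PSG 1 as its only baseline and takes no contribution from c4. Separately, any by-treatment comparison confined to period 2 has about four times the variance of the within-subject comparison, provided the two pairs of visits correlate equally.

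**What to change.** In 1.11 and 8.5:

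1. Make the treatment comparison for scales and wearable outcomes a within-subject comparison of end-of-period values (Office Visit 3 against 5; final week of each period) with a period term, in place of the between-group ANCOVA.
2. If the Office Visit 4 to 5 and washout-week contrasts are kept, present them as descriptive only, without significance tests, and label them as confounded with prior treatment.
3. Add a descriptive summary, by sequence, of change from baseline to Office Visit 4 and to the washout week. For SGI-C and CGI-C, which are already anchored to study start, this is the Office Visit 4 rating itself. Do not use it as a pre-test to choose the analysis.

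The cost is wording; all the data are already collected. There are two downsides. The period-specific baseline is no longer used for inference. The within-subject estimate also still carries half of any carry-over that lasts to Office Visit 5, which the period term does not remove. The by-sequence summary helps to show whether that is a worry.

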For all subjects who meet non-PSG eligibility criteria, the screening/baseline PSG will be completed within 3 weeks (0-21 days) after Office Visit 1. This will be performed at EvergreenHealth's Sleep Disorders Center according to their standard clinical protocol. At a minimum, PSG interpretation will report latency to persistent sleep (LPS), wakefulness after sleep onset (WASO), sleep efficiency, and apnea-hypopnea index (AHI). In addition to screening for eligibility, the screening PSG will provide baseline values for the PSG variables of interest. Eligibility will be confirmed based on the results of the PSG according to the eligibility criteria listed in section 5.1.

4.4 Treatment Period 1

4.4.1 Office Visit 2

For those who satisfy all eligibility criteria, Office Visit 2 will occur within 7-14 days after the screening PSG. Medications will be reviewed again to ensure stability of the PD medication regimen and absence of any prohibited medications.

Following confirmation of eligibility, an eligible patient will complete the baseline assessments of the MDS-UPDRS (only parts 1, 2, and 4; the data from part 3 that was collected at Office Visit 1 as a part of the screening will serve as the baseline for this measure), ISI, ESS, BDI, and BAI during Office Visit 2. Data from the wearable sleep monitor will be collected.

An eligible patient will be randomized in a 1:1 randomization scheme to receive suvorexant 10 mg qhs or placebo. Randomization will occur at the research pharmacy of EvergreenHealth using

a computer-generated randomization list. The pharmacist will maintain a codebook indicating the treatment allocation of each subject. Study medication will be delivered by the research pharmacist to the research study staff from the research pharmacy (a separate locked room containing only research medications). The investigating physicians, research coordinator(s), and study subjects will be blinded as to treatment arm until the code is broken. The randomization code may be broken by the investigator only in a medical emergency. The reasons for such an emergency will be documented carefully. The subjects will receive identical appearing active or placebo study medication tablets, with identification known only to the research pharmacist.

4.4.2 Phone Visit 1

Phone Visit 1 will occur 3-4 days after Office Visit 2 to review safety and tolerability through questioning about adverse events.

4.4.3 Phone Visit 2: Titration in Treatment Period 1

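### The superiority test in a two-period crossover is left to a between-group ANCOVA or any other method; the crossover model should be written down

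*Combined protocol and SAP*

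**What the plan says.** The design is a crossover. Section 1.5: "Subjects will then be crossed over into the alternate treatment group". Section 4.6.1: "All subjects who received study drug in treatment period 1 will be given placebo in treatment period 2", and the reverse for the other group. PSG 2 closes period 1 (4.4.5) and PSG 3 closes period 2 (4.6.5). Section 8.2 reaches its target of 20 per arm through the design: "This will be achieved by having 20 subjects complete both treatment and placebo arms using a crossover study design".

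The analysis text is the same sentence in 1.11 and 8.5: "Outcome measures will be compared between groups using analysis of covariance (ANCOVA) or other method as deemed appropriate by the consulting statistician". It is followed by "Demonstration of superiority will depend on achieving statistical significance for the primary endpoint", two-sided at 0.05. For PSG variables, 8.5 otherwise lists only two separate percentage-change summaries, PSG 1 to PSG 2 and PSG 1 to PSG 3, by treatment.

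The only PSG baseline is PSG 1 (4.3.2): "the screening PSG will provide baseline values for the PSG variables of interest". The rating scales are repeated at Office Visit 4 "To serve as baseline scores for treatment period 2", but there is no PSG at that visit.

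**The concern.** In a two-period crossover the treatment effect is estimated within subject, and its standard error should reflect the correlation between a subject's two treatment nights. The analysis sections never use that pairing. They compare groups, section 8.2 counts subjects per arm, and section 8.4 describes placebo and drug groups as a parallel-group trial would. A statistician who follows the one named method literally would put 40 PSG results (20 subjects, two nights each) into an ANCOVA on PSG 1 and treat them as independent.

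Two things are at stake. One is the superiority decision, which rests on this single test. The other is the confidence interval and variance passed to the larger study, since 1.11 says that any effect seen may be used to power one.

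**Working it through.** **The plan's own figure.** 20 subjects × 2 treatments = 40 PSG results, 20 per arm. This matches the count in 8.2. It comes from a level-of-evidence convention and not from a power calculation, so there is no stated power to reproduce.

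**Assumptions (not in the documents).** Sleep efficiency has a common SD on each PSG night, taken as 1. The correlation of PSG 1 with each treatment PSG is rb, and the correlation between PSG 2 and PSG 3 is rw. There are 10 subjects per sequence and no period effect.

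**Step 1: true variance.** The estimate is the mean on drug minus the mean on placebo, from the same 20 subjects:
Var = 2(1 − rw)/20.

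**Step 2: variance reported by the literal ANCOVA.** With treatment and PSG 1 in the model and 40 rows taken as independent:
Var = 2(1 − rb²)/20, on 37 df.

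**Step 3: ratio.** Reported over true = (1 − rb²)/(1 − rw). When all correlations equal ρ this is (1 − ρ²)/(1 − ρ) = 1 + ρ.

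**Step 4: interval width.** Relative width = √(1 + ρ) × t(37 df)/t(18 df) = √(1 + ρ) × 2.026/2.101.

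**Step 5: power and type I error.** The effect is set so that the crossover test (18 df) has 80% power. For ρ = 0.5: 0.662/0.224 = 2.96 standard errors. Error rates come from 40,000 simulated trials per setting.

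| ρ | True SE | Reported SE | Relative CI width | Effect (SD) | ANCOVA type I error | ANCOVA power | Crossover power |
|---|---|---|---|---|---|---|---|
| 0.3 | 0.265 | 0.302 | 1.10 | 0.784 | about 2.8% | about 74% | 80% |
| 0.5 | 0.224 | 0.274 | 1.18 | 0.662 | about 1.9% | about 69% | 80% |
| 0.7 | 0.173 | 0.226 | 1.26 | 0.513 | about 1.3% | about 63% | 80% |

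The crossover test's own type I error stays at about 5%. The power loss disappears at low correlation: at ρ = 0.1 the two powers are 79.4% and 79.6%.

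**Step 6: one simulated dataset.** The mixed model, the ANCOVA with subject and period factors, and the period-adjusted paired test all give an estimate of 6.356 with SE 2.215 (t = 6.356/2.215 = 2.87 on 18 df). The ANCOVA without those terms gives the same estimate with SE 2.708 (t = 6.356/2.708 = 2.35). With balanced sequences, only the error bar changes.

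**Step 7: can the error run the other way?** By step 3, the literal ANCOVA is anti-conservative only if rw < rb². With rb = 0.7 and rw = 0.4, simulated type I error is 6.9%. It can also exceed 5% when a chance sequence imbalance meets a large period effect. A 14/6 split with a 1 SD period effect (ρ = 0.5) gives about 16%; under simple randomization a split that uneven or worse has probability 11.5%. Averaged over all splits from simple randomization, for ρ from 0.3 to 0.7, type I error is about 1% to 3% with no period effect, 2.5% to 3.5% at 0.5 SD and 5% to 6% at 1 SD.

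**The case against.** The strongest reply is that the plan does not prescribe the wrong model. An ANCOVA with subject and period as factors is a valid crossover test, and the wording allows it. That stands: the defect is an unstated model whose literal reading is wrong, not a plan that excludes the right one. The study is also an exploratory pilot with no power target (1.11, 8.2), which lowers the stakes. But both sections keep a superiority rule at 0.05, so the test should be defined.

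A reader might go further in four ways that the documents do not support.

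- **The false-positive rate is inflated.** This needs special conditions (step 7), none of them in the documents. Section 6.2 does not mention blocking but does not exclude it, and the average over simple randomization is roughly nominal or below. Subjects are also selected on PSG 1 (5.1), which tends to weaken its correlation with later nights and so favours the conservative side.
- **The method may be picked by its result.** Section 8.1 keeps the data blinded throughout the analysis. This limits such a choice, though it does not say which model is used.
- **Period 1 alone might be analysed.** That would leave about 10 per arm, against the 20 per arm that 8.2 counts from both periods, and 8.5 carries PSG 3 into the efficacy analysis.
- **The endpoint's form is unsettled.** Section 4.1 speaks of change, while 1.10.1 and 7.2.1 give the value itself. In a within-subject comparison PSG 1 cancels, so the two give the same result. Percentage change appears only in the summaries.

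**Conclusion.** The point holds as a gap that should be fixed. Sections 1.11 and 8.5 do not state the crossover model behind the single superiority test, and the only named method, taken literally, gives a wrong standard error for paired data. Under equal correlations of 0.3 to 0.7, balanced sequences and no period effect, the result is an over-conservative test that loses roughly 6 to 17 percentage points of power (80 − 74 to 80 − 63), with an interval 10% to 26% too wide. With balanced sequences the point estimate is unaffected.

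That the model is unstated is certain. The sizes are illustrative, because the documents give no correlation, SD or period effect. A general claim of inflated type I error is not supported.

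**What to change.** In 1.11 and 8.5, for the primary endpoint, replace the ANCOVA sentence with:

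> *PSG sleep efficiency (percentage points) at PSG 2 and PSG 3 will be compared within subject using a linear mixed model with fixed effects for treatment, period and sequence and a random subject effect; the treatment contrast, with its 95% CI, is the test of superiority at two-sided 0.05.*

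A period-adjusted paired analysis is equivalent with complete data and would also do. The mixed model has the advantage of keeping randomized subjects who have only one post-baseline PSG. This fits the intent-to-treat statement in 8.3, given that 5.4 allows withdrawal and replacement. Keep the percentage-change tables as descriptive, and report the within-subject SD for planning the larger study.

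The cost is wording only: no added visits, data or subjects. The change should be made before unblinding.
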